10.4.3 Physical examination

Physical examination findings will be recorded in the eCRF at Screening. Clinically relevant changes in subsequent physical examinations will be reflected as AEs if not related to SLE. If physical examination findings are related to SLE, they will be documented within the BILAG 2004 and/or SLEDAI-2K assessment eCOA. The outcome of physical examinations and the interim medical history must be documented in source documentation.

A complete physical examination will include, at a minimum, general appearance; ear, nose, and throat; eyes, hair, and skin; and assessments of the respiratory, cardiovascular, gastrointestinal, musculoskeletal, hepatic, and neurological (including focused assessment of reflexes, sensitivity, and muscle strength) systems and mental status. Height (only at Screening) and weight will also be measured and recorded.

Results of physical examination abnormalities will be listed.

10.4.4 Assessment of Suicidal Ideation and Behavior

Suicidal ideation and behavior will be assessed using the C-SSRS (Columbia Suicide Severity Rating Scale). This scale will be used at Screening and Visits 2 through 15 to assess suicidal ideation and behavior.

At Screening, participants will be asked to assess suicidal ideation and behavior for their lifetime and for the past 6 months and for the past 2 years (respectively) prior to Screening.

At Visit 2 through Visit 15, participants will be asked to assess suicidal ideation and behavior since the last study visit.

The C-SSRS includes 10 categories with binary responses (yes/no):

Category 1: Wish to be dead

Category 2: Non-specific Active Suicidal Thoughts

Category 3: Active Suicidal Ideation with Any Methods (Not Plan) without Intent to Act

- Category 4: Active Suicidal Ideation with Some Intent to Act, without Specific Plan
- Category 5: Active Suicidal Ideation with Specific Plan and Intent
- Category 6: Preparatory Acts or Behavior
- Category 7: Aborted Attempt
- Category 8: Interrupted Attempt
- Category 9: Actual Attempt (non-fatal)
- Category 10: Completed Suicide

The C-SSRS also includes the following:

- Features (which should be rated with respect to the most severe type of ideation (ie, 1-5 from above, with 1 being the least severe and 5 being the most severe), since last visit which defines the intensity of ideation (frequency, duration, controllability, deterrents and the reason for ideation)
- Suicidal behavior (actual attempts, has subject engaged in non-suicidal self-injurious behavior?, interrupted attempt, aborted attempt, preparatory acts or behavior, suicidal behavior, suicide and for actual attempts only: actual lethality/medical damage, potential Lethality).

Endpoints based on the above categories are defined as:

Suicidal ideation: A “yes” answer at any time during treatment to any one of the 5 suicidal ideation questions (Categories 1-5) on the C-SSRS.

Suicidal behavior: A “yes” answer at any time during treatment to any one of the 5 suicidal behavior questions (Categories 6-10) on the C-SSRS.

Suicidal ideation or behavior: A “yes” answer at any time during treatment to any one of the 10 suicidal ideation and behavior questions (Categories 1-10) on the C-SSRS.

A listing will be provided including all data for only those participants who have a ‘Yes’ response in any category at any visit. The listing will be by visit and will indicate the reference timepoint upon which each C-SSRS category was evaluated (eg, ‘Lifetime’ for Screening visit, and ‘Previous visit’ for all visits after Screening).

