9.2 General statistical considerations

9.2.1 General presentation of summaries and analyses

Statistical analysis and generation of tables, figures, study participant data listings, and statistical output will be performed using SAS® Version 9.4 or higher.

All original and derived parameters will be listed and described using summary statistics. For continuous parameters, number of participants with available measurements, mean, standard deviation (SD), median, minimum and maximum and for categorical parameters, number of participants and percentages (to one decimal place) in each category will be presented.

All descriptive statistics will be presented by treatment where applicable, including columns for all treated participants and all participants on demographics, baseline characteristics, and AE displays, and using the available data for the study population as observed. Summaries of concentration data will be based on geometric mean and geometric standard deviation instead of arithmetic versions. All tabulations will be sorted by treatment, parameter and visit (including time relative to dosing if applicable, unless otherwise stated). Only scheduled visits and times relative to dosing will be included in the tabulation.

Categorical data will be summarized by visit and treatment group, including columns for all treated study participants and all study participants on demographics, baseline characteristics, and AE displays, using the number and percent of study participants in each category.

Percentages will be based on the corresponding population size (ie, the denominator of percentages should match the sample size in the column header), unless otherwise noted via footnote in the applicable summary table.

Statistical tests of efficacy variables will be presented as 2-sided p-values. P-values will be rounded to 4 decimal places. P-values less than 0.0001 will be presented as “<0.0001” and p-values greater than 0.9999 will be presented as “>0.9999.”

Handling of multiplicity for the primary and key secondary efficacy variables is discussed in Section 9.4. All other efficacy variables will be considered secondary or exploratory and will be assessed at a nominal 2-sided $\alpha=0.05$ significance level.

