Exclusion	28a	
Study participant has history of a suicide attempt within the 5 years prior to the Screening Visit or has had suicidal ideation in the past 6 months as indicated by a positive response ("Yes") to either Question 4 or Question 5 of the "Screening/Baseline" version of the Columbia Suicide Severity Rating Scale (C-SSRS) at Screening.
 
Note:
 
 • In case a study participant responds to Question 9 in PHQ9 [REDACTED] [REDACTED] [REDACTED] [REDACTED] [REDACTED] the severity of the suicidal ideation needs to be adequately assessed with the C-SSRS rating scale • In case of history of a suicide attempt more than 5 years ago the absence of concurrent suicidal ideation and/or severe depression should be confirmed by a mental healthcare practitioner before enrolling into the study. 	To protect study participants' well-being. Study participants with SLE have an increased risk for depression and suicidality. Some biotherapeutic immunomodulators are suspected to increase the risk for suicidality.

Criterion	N	Content	Justification
Exclusion	29a	
Study participant has ≥ 3 times the ULN alanine aminotransferase (ALT), aspartate aminotransferase (AST), or alkaline phosphatase (ALP), or $>$ULN bilirubin ($\geq 1.5 \times$ULN bilirubin if known Gilbert's syndrome), except in the case where the abnormal test values are ascribed to SLE hepatitis.
 
 • If study participant only has $>$ULN, but $<1.5 \times$ULN bilirubin, fractionate bilirubin to identify possible undiagnosed Gilbert's syndrome (ie, direct bilirubin $<35\%$) should be assessed, except in the case where the abnormal test values are ascribed to SLE hepatitis or hemolytic anemia, in the opinion of the Investigator. • In case of a suspected SLE hepatitis, eligibility must be discussed with the Medical Monitor. • If study participant has a result of ALT, AST, or ALP that is $>$ULN but that does not meet the exclusion limit at Screening, a repetition of the lab assessment is recommended to judge the dynamic of the increase but is in the Investigator's discretion considering the medical history of the study participant. In case of a further clinically relevant increase (with a value that still doesn't meet the exclusion limit), inclusion of the study participant must be discussed with the Medical Monitor. 	To protect study participants' well-being. Severe liver dysfunction could impact the metabolism of DZP

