3 DATA ANALYSIS CONSIDERATIONS

3.1 General presentation of summaries and analyses

Statistical analysis and generation of tables, figures, study participant data listings, and statistical outputs will be performed using SAS® Version 9.4 (SAS Institute, Cary, NC, USA).

For continuous parameters, number of participants with available measurements, mean, standard deviation (SD), median, minimum and maximum, and for categorical parameters, number of participants and percentages (to one decimal place) in each category will be presented in the summary tables. Changes from Baseline and/or percentage changes from Baseline will be presented where required.

All descriptive statistics will be presented by treatment group where applicable. All tabulations will be sorted by treatment, parameter and visit (including time relative to dosing if applicable, unless otherwise stated). Only scheduled visits and times relative to dosing will be included in the tabulation. The number of decimal places for continuous summary statistics should be based on level of precision captured in the source (eg, case report form (CRF), lab transfer, etc.) for non-derived variables. In general, for derived variables, min/max will be presented as collected in the source, and mean, SD, median have 1 additional decimal place with respect to the source.

Categorical data will be summarized by visit and treatment group, including column for all study participants in certain outputs (see Section 3.7 for details). Percentages will be based on the corresponding population size (ie, the denominator of percentages should match the sample size in the column header), unless otherwise noted via footnote in the applicable summary table.

Percentages will be presented to 1 decimal place. For data points with n=0 (ie, no participants in the applicable category), no value for percentage of participants will be displayed.

Missing observations will be counted and described in the reports unless otherwise specified. For the shift tables, the percentages will be based on non-missing records at Baseline and the related post Baseline time points.

Statistical tests of efficacy variables will be presented as 2-sided p-values. P-values will be rounded to 4 decimal places. P-values less than 0.0001 will be presented as “<0.0001” and p-values greater than 0.9999 will be presented as “>0.9999.”

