- (13) Incidence of thromboembolic TEAEs as confirmed by the adjudication committee
- (14) Incidence of TEAEs fulfilling the definition of MACE, defined as events coded to MedDRA PTs under the narrow SMQ Central nervous system haemorrhages and cerebrovascular conditions, narrow SMQ Ischaemic heart disease, and narrow SMQ Cardiac failure, as well as the following additional MedDRA PTs: Cardiac death, Angioplasty, Arterial angioplasty, Atherosclerotic plaque rupture and Intra-aortic balloon placement

[figure not shown]
- (15) Incidence of TEAEs starting on the day or the day after an infusion.
- (16) Incidence of infusion reaction TEAEs in participants with infusion reactions (as indicated by the investigator on the CRF)
- (17) Incidence of infusion reactions meeting Sampson's criteria of Anaphylaxis as determined by the investigator
- (18) Incidence of TEAEs suggestive of [REDACTED] based on the narrow SMQ for [REDACTED]
- (19) Incidence of [REDACTED] TEAEs based on narrow SMQ for [REDACTED] starting on the day or the day after an infusion
- (20) Incidence of [REDACTED] TEAEs based on narrow SMQ for [REDACTED] starting later than the day after an infusion
- (21) Incidence of TEAEs in SMQ Anaphylactic reaction where scope='Narrow'
- (22) Incidence of TEAEs suggestive of suicidal events based on Suicide/self-injury (SMQ)
- (23) Incidence of TEAEs suggestive of depressive or suicidal events based on depression and suicide/self-injury (SMQ)
- (24) Incidence of TEAEs in the SMQ depression and suicide/self-injury where scope=narrow
- (25) Incidence of non-serious TEAEs occurring in $\geq 5\%$ of participants within any individual treatment group (incidence is compared to the threshold prior to any rounding)
- (26) Incidence of non-serious TEAEs by relationship
- (27) Incidence of TEAEs leading to permanent study drug discontinuation or withdraw from the study, by relationship
- (28) Incidence of fatal TEAEs by relationship
- (29) Incidence of TEAEs excluding adverse events related to COVID-19 vaccines as determined by the investigator
- (30) Incidence of TEAEs by Decreasing Incidence of MedDRA Preferred Term
- (31) Incidence of TEAEs Suggestive of Herpes Zoster TEAEs by Medication Subgroup

Figures:

- Relative Risk of Most Frequent AEs (Preferred Term) – All TEAEs
- Relative Risk of Most Frequent AEs (Higher Level Term) – All TEAEs

Note: most frequent will include top 30 most frequent TEAEs

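### SAP 10.4.4 defines three on-treatment C-SSRS endpoints but names only a listing, so no visible output reports their incidence by arm

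*SAP*

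**What the plan says.** SAP 10.4.4 describes ten yes/no C-SSRS categories, assessed at Screening and at Visits 2 through 15. Screening asks about lifetime and recent history; every later visit asks about the time since the previous visit. The section continues: "Endpoints based on the above categories are defined as" suicidal ideation (Categories 1 to 5), suicidal behavior (Categories 6 to 10) and the combination, the last being a positive "answer at any time during treatment to any one of the 10 suicidal ideation and behavior questions (Categories 1-10) on the C-SSRS".

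The only output then named is this: "A listing will be provided including all data for only those participants who have a" positive response in any category at any visit. On its layout the SAP adds: "The listing will be by visit and will indicate the reference timepoint upon which each C-SSRS category was evaluated".

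Other relevant text:

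- Protocol 9.2.1: "All original and derived parameters will be listed and described using summary statistics".
- SAP 3.1: "Categorical data will be summarized by visit and treatment group, including column for all study participants in certain outputs".
- SAP 10.1, item 22: "Incidence of TEAEs suggestive of suicidal events based on Suicide/self-injury (SMQ". Items 23 and 24 extend this to the depression and suicide/self-injury SMQ.
- Protocol Appendix 13, in the rationale for exclusion criterion 28a, notes the raised risk of depression and suicidality in SLE and adds: "Some biotherapeutic immunomodulators are suspected to increase the risk for suicidality".

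**The concern.** An endpoint that is defined and never tabulated is a loose end in any plan. Here it concerns a safety question that the protocol itself raises, and an instrument given at all 15 visits. A listing gives neither a numerator nor a denominator by arm. A reader of the study report who wants to know what proportion of each arm had ideation on treatment would have to derive it from individual rows.

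The AE tables answer a related but different question. They count what was reported and coded as an adverse event, not what was scored on the scale.

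**Working it through.** The claim rests on text, so the check sets the relevant sections side by side.

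**1. Is there a C-SSRS table anywhere visible?** SAP 2.2, 3.1, 10.1 and 10.3 to 10.5, and protocol 8.2.5, 9.2.1 and 9.4.1, contain no count or percentage of the three endpoints by treatment group. SAP 10.4.4 itself is not redacted and refers to no other section for one.

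**2. Does listing-only fit the general rules?** Protocol 9.2.1 asks for derived parameters to be both listed and summarized. The three endpoints are derived parameters. The readable part of SAP Table 3-1, which records departures from the protocol, shows none for the C-SSRS.

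**3. How are comparable data handled?** SAP 10.4.1 (vital signs) and 10.4.2 (ECG) name number-and-percentage tables. SAP 10.3 says that HIV, hepatitis and tuberculosis tests are listed only, and gives the reason that they serve eligibility. For the C-SSRS the SAP gives neither a table nor a reason.

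**4. Do the AE tables fill the gap?** Under protocol 8.3 and Appendix 3, SLE manifestations become AEs only if they are serious. Neuropsychiatric disease is one of the nine BILAG systems. It follows that non-serious ideation that an investigator attributes to neuropsychiatric SLE can be positive on the C-SSRS, never become a TEAE, and so be absent from items 22 to 24. The protocol recognizes this kind of misattribution: section 4.1 has the IDMC look for neuropsychiatric events wrongly assigned to SLE.

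**5. Is the phrase about treatment precise enough to program?** Nominal days come from the protocol's schedule of activities: last dose Day 308 (Week 44), Visit 14 Day 336, Visit 15 Day 378.

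- Treatment period in SAP 10.1, item 10 (last infusion plus 28 days): 308 + 28 = Day 336. Visit 15 falls outside.
- TEAE window in SAP 10.1 (60 days after last dose): 308 + 60 = Day 368. Visit 15 asks about Days 336 to 378, that is 378 − 336 = 42 days. Of these, 368 − 336 = 32 lie inside the window and 378 − 368 = 10 outside.
- Visit 2 asks about the time since Screening, which is before the first dose.

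SAP 10.4.4 does not say which window applies, so a table would need that stated.

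**The case against.** The other side has several fair points.

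- **Suicidality is already tabulated.** A reader might infer that it is never shown by arm. That is not so: SAP 10.1, items 22 to 24, does this for TEAEs, and SAP 3.1 presents descriptive statistics by treatment group. In addition, under protocol 7.1.3 active ideation confirmed by C-SSRS Question 4 or 5, after the PHQ-9 item 9 trigger, leads to study medication being stopped. TEAEs leading to discontinuation are tabulated (items 8 and 9). This makes it less likely that the gravest ideation appears only on the scale. It does not reach Categories 1 to 3, and it still needs an AE to be recorded.
- **The listing is orderly.** A reader might infer that it blurs lifetime history with on-treatment answers. The SAP says otherwise: it is by visit and labels the reference timepoint. Lifetime answers are included but can be told apart.
- **The general rules might be enough.** SAP 3.1 and protocol 9.2.1 could be read as implying a table. They name none for the C-SSRS, and the specific section names only a listing, so a programmer working from 10.4.4 would produce only the listing.
- **No listed endpoint is lost.** The C-SSRS is not among the endpoints in protocol section 3 or SAP 2.2, and the sentence in Appendix 13 concerns some immunomodulators, not DZP. Both points stand and limit the weight of the concern.
- **Redaction.** SAP 13.19 (IDMC outputs) and the rationale for SAP Amendment 3 cannot be read and might hold a C-SSRS summary. This cannot be excluded.
- **Listing-only is used elsewhere,** for example for the TB questionnaire and physical examination. Those sections define no endpoints.

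**Conclusion.** The point holds as a minor gap. Three C-SSRS endpoints are defined, one listing is named, and no visible output gives their incidence by arm. This sits badly with protocol 9.2.1, and the SMQ tables only partly make up for it.

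The documents do not support reading this as a missing hypothesis test, because the safety analyses are descriptive. Nor do they support calling it a failure to analyze a protocol endpoint. No numerical size can be attached, since neither document gives an expected C-SSRS event rate.

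The conclusion assumes that no redacted section contains the table, and that some non-serious ideation may be attributed to SLE and so not reported as an AE. How often that would happen cannot be judged from the documents.

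**What to change.** In SAP 10.4.4, add one descriptive table on the Safety Set, by treatment group, giving n (%) for each of the three defined endpoints. Count only assessments made after the first dose, so that Screening and Visit 2 answers do not enter, and state whether Visit 15 counts as on treatment. Keep the listing as it is.

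A shift table from Screening to worst later category is not needed. It would set lifetime, 6-month or 2-year recall against recall since the previous visit, and it goes beyond the endpoints defined.

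The cost is one extra table from data already collected. If only a listing is really intended, the alternative is to delete the endpoint definitions and give the reason, but that would leave the scale without any by-arm summary.

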10.5 Tuberculosis (TB) Questionnaire: Evaluation of Signs and Symptoms of Tuberculosis

TB questionnaire data collected in the eCOA will be listed using the SS.

11 COVID-19 IMPACT

The following data to evaluate the impact of COVID-19 global pandemic on the study will be captured in the COVID-19 eCRF:

1. Impacted Visit
2. Impact Category
 - Visit not done
 - Visit performed out of window
 - Visit performed by video call
 - Visit performed by telephone
 - Temporary discontinuation of study drug
 - Permanent discontinuation of study drug

- Termination of study participation
- Other, specify

3. Relationship to COVID-19

- Confirmed COVID-19 infection
- Suspected COVID-19 infection
- General circumstances around COVID-19 without infection
- Other, specify

- A summary and a listing of impact of COVID-19 for any reason (including impact category and visit (timepoint)) by treatment arm using the FAS will be created
- A summary of impact of COVID-19 due to confirmed or suspected COVID-19 infection (including impact category and visit (ie, timepoint)) by treatment arm using the FAS will be created
- Summary of Overall Missed or Discarded Assessments (visits) by Key Endpoints (primary, key secondary and secondary endpoints)
- Summary of Covid-19 Impact by Impact Category: number of visits performed by video call or by phone

████████████████████ will be assessed in the scope of exploratory biomarker analysis as a separate analysis outside the scope of the SAP and will be summarized in a separate report.

This document cannot be used to support any marketing authorization application and any extensions or variations of the product.

This document contains neither recommendations nor conclusions of the U.S. Food and Drug Administration. It is the property of U.S. Food and Drug Administration or its contractors, and is being made available only to authorized FDA staff for official use.

ation

[figure not shown]
This
document
is
for
internal
use
only

This
document
is
for
internal
use
only

[figure not shown]
This

ation

This

This document cannot be used in
application and any extension
of this document is illegal.

This document is a draft and is not for distribution

[figure not shown]
This

This

[figure not shown]
This

This
document
is
for
internal
use
only

This

This document contains neither recommendations nor conclusions of the U.S. Food and Drug Administration. It is the property of U.S. Food and Drug Administration or its contractor, and is being made available only to assist in the conduct of clinical trials. It is the intent of the U.S. Food and Drug Administration that the clinical trial data contained in this document will not be subject to the Freedom of Information Act, 5 U.S.C. 552.

This document cannot be
submitted as part of an
application and a

This

This

This document cannot be used to support a
public application and any extensions

This document cannot be used to support publication and any extensions
PUBLICATION

This document contains confidential information and is the property of UCB. It is intended solely for the use of the individual or entity named on the cover page. It is not to be distributed without the express written consent of UCB.

This document cannot be used outside the current application and any extension thereof.

This document cannot be used in an application and any use is illegal.

ation

[figure not shown]

Authorization
hereof.

This document cannot
be used for any
application and
is not subject to
any form of
authorization
hereof.

Authorization
eof.

[figure not shown]
T

[figure not shown]
This document cannot be
submitted as part of an
application and a

This document cannot be PUBLIC COPY
application and any extensions or variations
ation

T

This document cannot be PUBLIC
application and any extensions or v

This document cannot be used to
PU
application and any extens.

This document cannot be PUBLIC
application and any extensions o

[figure not shown]
This document cannot be used
application and any exten

This document appears to be a redacted page from a statistical analysis plan for Dapirolizumab pegol. The page is mostly black, with a large diagonal watermark reading 'This document appears to be a redacted page from a statistical analysis plan for Dapirolizumab pegol'.

This document cannot be used in
application and any extension
of this document is illegal.

This document cannot be used for any application and any e

[figure not shown]
This document cannot be PUBLIC
application and any extensions o
ation

This document cannot be published in its current form.
application and any extensions

This document cannot be PUBLIC
application and any extensions

This
document
is
for
internal
use
only

This document contains confidential information
and is the property of UCB.

This

This document is the property of UCB and is to be used only for the purpose of the study. It is not to be reproduced, distributed, or disclosed outside the study without the prior written consent of UCB.

This document cannot be PUBLIC
application and any extensions
ation

This document cannot be used to support any manufacturing application and any extensions or variations of this document are not permitted without prior written approval from UCB. This document is for internal use only and is not intended for distribution outside UCB. It is the responsibility of the user to ensure that any use of this document complies with all applicable laws and regulations.

PUBLIC COPY

[figure not shown]
